### 4.2.4 Sensitivity analyses

Two sensitivity analyses are performed. Both sensitivity analyses challenge the primary estimand.

#### Sensitivity analysis 1

The primary analysis relied on the assumption that discontinuation of treatment prior to period 4 occurred completely at random. A sensitivity analysis challenging this assumption will be performed as follows. For subjects in FAS who discontinue treatment prior to the efficacy assessment period (period 4), the primary endpoint will be carried forward in term of both the number of clinically relevant asthma exacerbations observed in period 3 and the actual exposure time in period 3. This dataset using an LOCF-type approach is based on FAS and will be analysed using the same model specified for the primary efficacy analysis.

No missing data approach is defined for treatment discontinuations in period 4.

The datasets specified in this sensitivity analysis will be analysed using the same model specified for the primary efficacy analysis.

#### Sensitivity analysis 2

Subjects who discontinue treatment in period 3 are not included in the analysis and no missing data approach is applied for these subjects.

Missing data for subjects who discontinue treatment and withdraw from trial prematurely before the planned end of study will be multiple imputed from the completers in the placebo group, i.e. it is assumed that after discontinuation of treatment subjects will experience the same treatment effect as subjects treated with placebo. Subjects that discontinue treatment and complete trial are treated as completers and all observations until the end of the trial period are used in the analysis. There will be no imputations to or from these subjects.

The datasets specified in this sensitivity analysis will be analysed using the same model specified for the primary efficacy analysis.

### 4.2.5 Supportive analysis

As a supportive analysis, the primary efficacy endpoint will be analysed based on the PP using the same NB regression model as for the primary efficacy analysis and the same intercurrent event approach as for the primary estimand.

### 4.2.6 Additional analyses investigating the impact of Covid-19

Additional analyses, where a Covid-19 effect is applied, are performed for the primary and secondary estimands of the primary endpoint (see **Table 1**). The Covid-19 effect is representing either the period before or during Covid-19 (20-Mar-2020).

### 4.3 Secondary endpoint analyses

For all secondary endpoints (key secondary and additional secondary endpoints), no data collected after treatment discontinuation is used.

Type of document Document ID	Date: Version: Status:	11-Aug-2022 4.0 Final	ALK
INTERNAL USE	Page:	32 of 79	

### 4.3.1 Key secondary endpoints

#### 4.3.1.1 Definition of endpoints

• Proportion of days with nocturnal awakenings due to asthma requiring SABA rescue medication during the 14 days eDiary recording every 4 months after randomisation

The number of days with nocturnal awakenings due to asthma requiring SABA rescue medication as well as the total number of eDiary recordings are calculated, and the proportion of days with nocturnal awakenings due to asthma requiring SABA rescue medication is calculated as the number of days with nocturnal awakenings due to asthma requiring SABA requiring SABA rescue medication out of the total number of days recorded.

 Proportions of days with SABA use during the 14 days eDiary recording every 4 months after randomisation

The number of days with SABA use as well as the total number of eDiary recordings are calculated, and the proportion of days with SABA use is calculated as the number of days with SABA rescue medication use out of the total number of days recorded.

• Percentage predicted FEV1 assessed every 4 months after randomisation

The calculated percentage of predicted FEV1 (%) is analysed.

#### 4.3.1.2 Overview of analyses of key secondary endpoints

Table 2 gives an overview of the analyses of the key secondary endpoints including the handling of treatment discontinuations.

#### Table 2 Overview of analyses and handling of discontinuations for the key secondary endpoints

Endpoint	Estimand	Analysis set	Impact of Covid-19 effect included	Statistical method	Treatment discontinuations in efficacy period
Nocturnal awakenings	Primary	FAS	1) None 2) OP1, OP2	Marginal logistic regression	Included as observed
SABA use	Primary	FAS	1) None 2) OP1, OP2	Marginal logistic regression	Included as observed
Pred. FEV 1	Primary	FAS	1) None 2) OP1, OP2	MMRM	Included as observed

None = no Covid-19 effect analysed, Pred. = predicted percentage, OP1 = trial observation period before and including 20-Mar-2020 (before Covid-19), OP2 = trial observation period after 20-Mar-2020 (during Covid-19), OP1, OP2 = a Covid-19 effect is applied representing either the period before or during Covid-19. Included as observed = only observed data in the part of the period in which they are collected are used. If discontinuations occur, the observed values are included.

Type of document	Date:	11-Aug-2022	
Document ID	Version:	4.0	
	Status:	Final	
INTERNAL USE	Page:	33 of 79	

### 4.3.1.3 Main analytical approach

The key secondary endpoints will be compared between treatment groups using the primary estimand for the FAS population.

The proportion of days with nocturnal awakening which require SABA rescue medication over the 14 days eDiary assessment period (before V5, V6, V7, V8, V9, V10 and V11) will be modelled by a marginal logistic regression model with an unstructured working covariance matrix. The response variable is the number of days with nocturnal awakenings due to asthma requiring SABA rescue medication out of the total number of days recorded. Treatment, visit and treatment-by-visit interaction, age group (<12 years/≥ 12 years) and region will be included as fixed effects. Baseline proportions of nocturnal awakenings requiring SABA will be included as a covariate. The marginal model will be estimated using a generalized estimating equations (GEE) approach. The treatment effect on the logit scale is an average treatment effect across all visits and will be estimated as a contrast of parameters in the marginal model. For both the overall treatment effect and the effect per visit, the corresponding odds ratio for proportions of days with nocturnal awakening requiring SABA of active treatment relative to placebo will be presented together with the coherent p-value and 95% confidence limit.

The proportion of days with SABA use over the 14 days eDiary assessment period (before V5, V6, V7, V8, V9, V10 and V11) will be analysed by means of a marginal logistic regression model and a GEE estimation approach as described for "proportion of days with nocturnal awakening which require SABA".

Percentage predicted FEV1 assessed every 4 months after randomisation (at V5, V6, V7, V8, V9, V10 and V11) will also be analysed by means of an MMRM model. The response variable is the percentage predicted FEV1. Treatment, visit, treatment-by-visit interaction, age group (<12 years/ $\geq$  12 years) and region will be included as fixed effects. Baseline percentage predicted FEV1 (measured at visit 3) will be included as a covariate. Different residual errors for each treatment group will be specified and the within-subject correlated errors are modelled by an unstructured covariance. The treatment effect is the average treatment effect across all visits. The between treatment comparison will be performed by means of a t-test with Kenward-Roger degrees of freedom approximation (Kenward and Roger 1997). For both the overall treatment effect and the effect per visit, the resulting p-value will be reported together with the difference in adjusted means.

In addition, the absolute treatment estimates by visit and 95% confidence intervals will be plotted from the MMRM model.

4.3.1.4 Sensitivity analyses

None.

4.3.1.5 Supplementary analyses

None.

#### 4.3.1.6 Additional analyses investigating the impact of Covid-19

Additional analyses, where a Covid-19 effect is applied, are performed for each of the described analyses of the key secondary endpoints. The Covid-19 effect is representing either the period before or during Covid-19 (20-Mar-2020).

Type of document Document ID	Date: Version: Status:	11-Aug-2022 4.0 Final	
INTERNAL USE	Page:	34 of 79	

### 4.3.2 Additional secondary endpoints

#### 4.3.2.1 Overview of analyses of additional secondary endpoints

**Table 3** gives an overview of the analyses of the additional secondary endpoints including the handling of treatment discontinuations.

#### Table 3 Overview of analyses and handling of discontinuations for the additional secondary endpoints

Endpoint	Estimand	Analysis set	Statistical method	Treatment discontinuations in efficacy period
Time to first and recurrent severe asthma exacerbation	None	FAS	Cox prop. hazards regression a	Included as observed
Time to first and recurrent asthma exacerbation	None	FAS	Cox prop. hazards regression a	Included as observed
Severe asthma exacerbation rate	None	FAS	NB regression	Included as observed
Change from baseline FEV 1	None	FAS	MMRM	Included as observed
Scores b	None	FAS	MMRM	Included as observed
ACQ/ACQ-IA	None	FAS	MMRM	Included as observed
Global evaluations c	None	FAS	GLMM	Included as observed
Immunology d	None	FAS	MMRM	Included as observed

aIncluding the Andersen-Gill extension.

bScores include endpoints of scores of asthma VAS, asthma symptoms, rhinitis and rhinoconjunctivitis symptoms and symptomatic medication.

cGlobal evaluation of allergic rhinitis and global evaluation of allergic asthma.

dChanges from baseline in IgE, IgE-BF and IgG4 against D. pteronyssinus and D. farinae.

#### 4.3.2.2 Asthma exacerbations

Time to first severe asthma exacerbation and time to first clinically relevant asthma exacerbation will be analysed by means of a Cox proportional hazards regression analysis. The model includes treatment and age group (<12 years/≥ 12 years) as effects. Region is included as a random effect assumed to follow a gamma distribution. Thus, this is a shared Cox gamma frailty model. The treatment comparison is performed using a Likelihood Ratio test based on the Cox proportional hazards regression model. The estimated hazard ratio (HR) of active treatment compared to placebo will be presented together with 95% Wald's confidence limits.

The Cox proportional hazards regression analysis is supplemented by a Kaplan-Meier analysis on time to first severe asthma exacerbation and time to first clinically relevant asthma exacerbation.

Time to recurrent clinically relevant asthma exacerbation and time to recurrent severe asthma exacerbation in days from the start of the efficacy period will each be analysed by means of an Andersen-Gill (AG) extension of the Cox model for recurrent events (Andersen and Gill 1982).

Type of document Document ID	Date: Version:	11-Aug-2022 4.0	
	Status:	Final	
INTERNAL USE	Page:	35 of 79	

The Andersen-Gill model assumes that events are independent, and so robust standard errors are used to accommodate heterogeneity. A Robust Sandwich covariance matrix will be used for the regression coefficient estimators. The treatment comparison is performed using a Likelihood Ratio test based on the extension of the Cox proportional hazards regression model. The model will include treatment and age group (<12 years/ ≥12 years) as fixed effects. The estimated hazard ratio (HR) of active treatment compared to placebo will be presented together with 95% confidence limits. In case of few recurrent clinically relevant asthma exacerbations or few recurrent severe asthma exacerbations, the endpoint(s) will only be summarised descriptively.

The annualised rate of severe asthma exacerbations in period 4 will be analysed similar to the primary efficacy endpoint using a NB regression model as described in section **4.2.3**.

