Percentage predicted FEV₁ assessed every 4 month after randomisation will be analysed by means of a MMRM. The model includes treatment, visit and age group (<12 years/≥ 12 years) and country as fixed factors, the baseline percentage predicted FEV₁ as a covariate and subject as a random effect. Different residual errors for each treatment group will be speficied and the within-subject correlated errors is modelled as TOEP. A between treatment comparison will be performed by means of a t-test with Kenward-Roger degrees of freedom approximation. The resulting p-value will be reported together with the difference in adjusted means. In addition the relative difference will be reported together with 95% confidence limits calculated based on Fieller's theorem.

The average TCRS over the two week diary assessment (before V5, V6, V7, V8, V9, V10 and V11) will be analysed by means a MMRM. The analysis includes the square root transformed average TCRS as response variable; treatment, visit, and treatment-by-visit interaction, age group (<12 years/≥ 12 years) and country as fixed factors; the square root transformed baseline score as a covariate and subject as random effects. Different residual errors for each treatment group is specified. For each visit, the between treatment comparison will be performed by means of a t-test. The resulting p-value will be reported together with the difference in back-transformed adjusted means. As additional information the relative difference of the back-transformed adjusted means is reported together with 95% confidence limits. The latter is calculated based on Fieller's theorem.

The average rhinitis DSS, the average rhinitis DMS, the average total combined rhinoconjunctivitis score, the average rhinoconjunctivitis DSS, the average rhinoconjunctivitis DMS will be analysed using a similar MMRM model as described for the average TCRS.

The average asthma DSS score and ACQ/ACQ-IA will also be analysed by means of a MMRM model.

Time to first severe asthma exacerbation and time to first clinically relevant asthma exacerbation will be analysed by means of a Cox proportional hazards regression analysis. The model is stratified for country and includes treatment group as a factor.

The severe asthma exacerbations will be analysed by means of a NB regression model with treatment group, agegroup (<12 years/ \geq 12 years) and country as factors and the logarithm of the duration time in years in period 4 as an offset value.

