### 4.1.1 Considerations regarding countries/region

Variation between countries/region in the primary endpoint is expected and may result from variation in geography and thus HDM exposure, variation in standard treatment procedures and from possible differences in conduct of the trial protocol. Variation between sites (centres) is also expected but is assumed to be small compared to the variation between countries and regions.

To ensure a balanced dataset for the primary endpoint, countries are pooled to regions. Three regions are defined (west: DEU, ESP, FRA, GBR and USA; central: POL; east: BGR, HUN and RUS). The region variable is used instead of country for all analyses, where a country/region factor is applied.

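### Region enters the exacerbation analyses in three different ways: fixed effect in the rate models, three-level gamma frailty in the time-to-first models, absent from the Andersen-Gill models

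*SAP*

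**What the plan says.** SAP 4.1.1 states: "Variation between countries/region in the primary endpoint is expected and may result from variation in geography and thus HDM exposure". It gives differences in standard treatment and in trial conduct as further reasons. Countries are then pooled: "Three regions are defined (west: DEU, ESP, FRA, GBR and USA; central: POL; east: BGR, HUN and RUS". Region replaces country wherever a country or region factor is used.

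The exacerbation endpoints use that variable as follows.

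- **Rates (SAP 4.2.3, and 4.3.2.2 for severe events):** negative binomial regression with treatment, age group and region as fixed effects.
- **Time to first event (SAP 4.3.2.2):** Cox model with treatment and age group, plus "Region is included as a random effect assumed to follow a gamma distribution". The SAP adds: "Thus, this is a shared Cox gamma frailty model".
- **Recurrent events (SAP 4.3.2.2):** Andersen-Gill model. "The model will include treatment and age group (<12 years/ ≥12 years) as fixed effects". "A Robust Sandwich covariance matrix will be used for the regression coefficient estimators". No fixed effect, stratum or frailty for region is listed.

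For the time-to-first endpoints, Protocol 15.8 had: "The model is stratified for country and includes treatment group as a factor". It gave no model for the recurrent endpoints. SAP 4.8 records the move to a gamma random effect without a reason and does not mention the recurrent-event models.

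**The concern.** The same events, in the same subjects, are analysed with three treatments of a factor that the SAP itself expects to matter. Two of the three choices are hard to justify.

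A shared frailty suits many clusters. With three, the data say almost nothing about the spread of the frailty distribution, and the model estimates a nuisance parameter that nobody needs. If that variance is estimated at zero, the fitted model makes no region adjustment. SAP 7.2.3 has a fallback for a Cox model that fails to converge, but none for a frailty variance of zero.

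In the Andersen-Gill models, variation between regions stays in the error. The sandwich covariance gives valid standard errors for dependent events within a subject. It does not recover the precision that adjustment for region would give.

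At stake are a little precision and a consistent set of exacerbation analyses.

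**Working it through.** No figure in the plan depends on this point, so there is none to reproduce. Three checks were made.

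**1. What three regions can tell about a variance.** Treat the three region effects as directly observed, which is the most favourable case. A variance from J clusters has J - 1 degrees of freedom.
- J = 3: relative standard error sqrt(2/2) = 100%. The 95% limits are 2/7.378 = 0.27 to 2/0.0506 = 39.5 times the estimate.
- J = 9 (the countries before pooling): 0.46 to 3.67 times the estimate.

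**2. Precision lost by omitting region from the recurrent-event model.**

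Inputs from the documents:
- Subjects: 533 randomised (SAP 1.2) less 9 at site 613 (SAP 3.1) = 524, or 262 per arm.
- Follow-up: 608 days (Protocol 15.2.1), so T = 608/365 = 1.67 years.
- k = 0.7 (SAP 5) and rate ratio 0.7 (Protocol 15.2.1).

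Assumed: the region rates, equal region shares, full follow-up, and k = 1 as an alternative.

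Let m be the mean placebo rate times T, and C² the squared coefficient of variation of the region rates. With a constant rate the Andersen-Gill model behaves as a Poisson rate model with robust variance. The variance of the log ratio is then proportional to
- with region: 1/m + 1/(0.7m) + 2k(1 + C²)
- without region: the same plus 2C²

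so the variance ratio is 1 + 2C² / [1/m + 1/(0.7m) + 2k(1 + C²)].

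- *2-fold spread (0.2, 0.3, 0.4 per year).* C² = [(0.01 + 0 + 0.01)/3]/0.09 = 0.074; m = 0.3 × 1.67 = 0.50. With k = 0.7: 1 + 0.148/(2.00 + 2.86 + 1.50) = 1.023. With k = 1: 1.021.
- *4-fold spread (0.15, 0.3, 0.6 per year).* C² = [(0.04 + 0.0025 + 0.0625)/3]/0.1225 = 0.286; m = 0.35 × 1.67 = 0.58. With k = 0.7: 1 + 0.571/(1.71 + 2.45 + 1.80) = 1.096. With k = 1: 1.085.
- *1.4-fold spread (0.25, 0.30, 0.36 per year).* C² = 0.022; ratio 1.006 to 1.007.

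Simulation of this model (600 trials, 262 per arm, k = 0.7 to 1) gave 1.02 for the 2-fold and 1.08 to 1.09 for the 4-fold spread. Early stopping lowers m and with it the ratio.

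The loss grows with the event rate. A second simulation used 524 subjects, k = 0.7, region shares 30/40/30, 20% stopping early and random region effects. Robust standard errors without and with region were:
- 0.166 and 0.165 at 0.3 events per year with region variance 0.09: ratio (0.166/0.165)² = 1.01.
- 0.116 and 0.108 at 1.4 per year with region variance 0.36: ratio (0.116/0.108)² = 1.15.

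Over all settings the estimated ratio was 0.69 to 0.70 with or without region, and adding region changed power by -0.3 to +2.3 percentage points.

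**3. What the three-region frailty does to the hazard ratio.** In the second simulation, with a constant-hazard version of the time-to-first model:
- True variance 0.09: median estimate about 0.02, with 95% of estimates between about 0 and 0.16-0.20.
- True variance 0.36: median 0.11 to 0.13, with 95% between about 0 and 0.67-0.75.
- The estimate fell below 0.001 in 6% to 34% of runs, depending on the setting.
- The hazard ratio with a frailty and with fixed region differed by at most 0.001 on average. The largest difference in a single run was 0.037 in the log hazard ratio.

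**The case against.** The strongest reply is that nothing of substance changes. Treatment is randomised, so leaving region out does not materially bias the treatment effect. A badly estimated nuisance variance is not a badly estimated hazard ratio. The endpoints have no estimand (SAP 1.1.9) and are outside the hierarchy (SAP 2.1). All of this stands and limits the size of the point.

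Three stronger readings are tempting and are not supported.

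- *Whether region is adjusted for is a matter of chance.* A near-zero variance occurs mainly when there is little to adjust for. With fixed region rates, the first-event frailty variance fell below 0.001 in 46-52% of simulated trials at a 1.4-fold spread, 8-11% at 2-fold and none at 4-fold. In those near-zero runs the log hazard ratio without region differed from the fixed-region one by 0.008 on average (maximum 0.054).
- *The hazard ratios cannot be compared with the rate ratios.* A first-event hazard ratio and an all-events rate ratio are different quantities however region is handled. For recurrent events, where comparison is natural, the estimate is the same with and without region.
- *Region was removed from the planned recurrent-event analysis.* The protocol had no model for these endpoints, so there was no term to remove. The change to the time-to-first model is declared in SAP 4.8, and the SAP states approval before unblinding. What is missing is a reason.

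It is also fair that stratifying the Cox-type models alone would still differ in form from the rate models. A fixed effect would make all of them match.

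**Conclusion.** The point holds as a minor inconsistency with a nearly free improvement. The SAP expects region to matter, adjusts for it in the rate models, uses a frailty that three regions cannot support in the time-to-first models, and has no region term in the recurrent-event models.

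The treatment estimates barely move. Omitting region from the Andersen-Gill models costs about 1-2% of variance at a 2-fold spread and up to about 8-9% at a 4-fold spread, with rates near 0.3 per year. The largest simulated cost was about 15%, at 1.4 events per year with a large region variance.

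These sizes rest on assumed region rates, region shares and early stopping, because the documents give no event rates or subject numbers by region. The formula and simulations also assume constant event rates over time. No conclusion about the primary or key secondary endpoints depends on this.

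**What to change.** In SAP 4.3.2.2:

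- Replace the gamma frailty in the time-to-first Cox models with the three-level region, either as a fixed effect (matching the negative binomial models) or as a stratum (as the protocol did by country).
- Add the same region term to both Andersen-Gill models.
- Keep treatment and age group in all of them.
- Record the change and its reason in SAP 4.8, and mention the recurrent-event models there.

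The fixed effect has the advantage that all exacerbation models then treat region alike. Before choosing strata, check blinded event counts by region, particularly for severe events. SAP 4.3.2.2 itself allows for few recurrent events, and thin strata would lose some information.

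The cost is a sentence or two of text and one model term or STRATA statement per model. Region is already derived for the other analyses. The change should be made before unblinding.
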